## 5.2 Efficacy Evaluations

MVPA (>100 steps per minute) is the primary endpoint to evaluate efficacy and will be obtained via Fitbit and W2H. Fitbit data collected through W2H will include step count, heart rate, manually logged activities, and sleep data, if available due to participant choosing to wear the Fitbit at night. MVPA will be calculated by W2H.

### **5.3 Safety Evaluations**

Participants will be fasting for a minimum of 12 hours prior to on site study visits. This may cause hunger pangs, upset stomach, headache, or light-headedness. If the participant shows any signs of clinical instability or definitively decides to discontinue participation, the study visit will be ended.

The patient will be notified of any clinically relevant abnormal test result(s) performed, by mail and or by phone. It will be recommended that results, especially abnormal results, be discussed by the guardian with the participant's primary care physician.

## 6 STATISTICAL CONSIDERATIONS

### 6.1 Primary Endpoint

We will determine the main and interactive effects of intervention components on mean daily MVPA during week 12 of the intervention.

### 6.2 Secondary Endpoints

Secondary endpoints include main and interactive effects of intervention components on mean steps per day during week 12 of the intervention, and change from visit 1 to visit 5 in:

- body mass index Z-score,
- hemoglobin A1c,
- fasting insulin,
- fasting glucose,
- fasting triglycerides, LDL, HDL, and
- liver enzymes (AST, ALT)

### 6.3 Exploratory Measures

Self-reported behavioral and motivational measures will be collected to use as covariates in multivariable analysis, as well as for exploratory correlational analyses. These include:

- Delay discounting tendency (k)
- Relative autonomy index
- Healthy eating inventory
- Smartphone-collected step count

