### 4.3.2 Visit 2 (Phone)

- Randomize to 1 of 16 experimental conditions

Experimental Condition	Text	Ramped goal	Incentive Framing	Goal time period
1	+	+	+	+
2	+	+	+	-
3	+	+	-	+
4	+	+	-	-
5	-	+	+	+
6	-	+	+	-
7	-	+	-	+
8	-	+	-	-
9	+	-	+	+
10	+	-	+	-
11	+	-	-	+
12	+	-	-	-
13	-	-	+	+
14	-	-	+	-
15	-	-	-	+
16	-	-	-	-

**Figure 2.**  $2^4 = 16$  experimental conditions

- Call participant to:
  - Review assigned step count goal
  - Explain financial incentive structure
  - Troubleshoot concerns related to Fitbit or text messages
  - If not eligible based on run-in: inform participant of study completion and request return of Fitbit via prepaid envelope

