#### 4.4 12-Week Intervention

##### 4.4.1 Dietary recalls (phone)

- 2 weekday, 1 weekend recall during weeks 1-2 of intervention: 3 x 30 minutes each

##### 4.4.2 Visit 3 (phone), Intervention Week 2

- Assess possible adverse events

##### 4.4.3 Visit 4 (phone), Intervention Week 6

- Assess possible adverse events

- Medical Record Review
- Troubleshoot any concerns related to Fitbit or text messages

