### 5.1.6 Dietary Recalls

During weeks 1-2 of the intervention, three 24-hour (2 weekday, 1 weekend) dietary recall interviews of participants will be conducted by a Children's Hospital of Pittsburgh registered dietitian via phone or in-person. Reported intake will be entered into a nutrition application (e.g. CalorieKing), without any patient-identifying information, in order to determine nutrition information including calories, protein, saturated fat, fatty acids, added sugar, and sodium. These data will be used to calculate the Healthy Eating Index score, (Krebs-Smith, Pannucci et al. 2018) using the scoring standards listed in **Figure 3**.

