**Table 1. Analysis plan**

Outcome	Analysis/statistical test
MVPA min/day: baseline vs 6 and 12 weeks ( primary outcome )	Mean/SD or median/IQR, ANOVA/ANCOVA
MVPA min/day: baseline vs 6 and 12 weeks	% of days with $\geq 60$ min/day, Fisher's exact test
MVPA min/day: average per week of intervention	% of days with $\geq 60$ min/day, Fisher's exact test
Steps/day: baseline (2 nd -week of run-in) versus 6 weeks and 12 weeks	Mean/SD or median/IQR, ANOVA/ANCOVA
Steps/day: baseline (2 nd -week of run-in) versus 6 weeks and 12 weeks	% of days with $\geq 10,000$ steps/day, Fisher's exact test
Steps/day: average per week of intervention	% of days with $\geq 10,000$ steps/day, Fisher's exact test
Body mass index Z-score	Mean/SD or median/IQR, ANOVA/ANCOVA
Hemoglobin A1c, insulin, glucose, triglycerides, LDL, HDL, AST, ALT	Mean/SD or median/IQR, ANOVA/ANCOVA
Hemoglobin A1c	% $<5.7\%$ , $5.7\text{-}6.4\%$ , $\geq 6.5\%$ , Fisher's exact test
Healthy Eating Index	Mean/SD or median/IQR, ANCOVA covariate, Pearson/Spearman correlation with demographic variables
Measure of delay discounting, k , derived from MCQ	Mean/SD or median/IQR, ANCOVA covariate (visit 1 measure), Pearson/Spearman correlation with demographic variables, paired t-test or Wilcoxon signed rank test to assess whether baseline and follow-up measures differ
Relative Autonomy Index (RAI) from BREQ-3	Mean/SD or median/IQR, ANCOVA covariate (visit 1 measure), Pearson/Spearman correlation with demographic variables, ANOVA/ANCOVA to assess change from visit 1 to 5 by experimental factor
PACE+: number of days with at least 60 minutes of activity per day in (a) past 7 days and (b) typical week	Mean/SD or median/IQR, Pearson/Spearman correlation with demographic variables and with number of days with MVPA $\geq 60$ minutes at baseline and week 12
Steps/week on smartphone activity tracker	Pearson/Spearman correlation with Fitbit-measured steps/week

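### The Healthy Eating Index is measured only after randomisation, yet Table 1 (Analysis plan) makes it an ANCOVA covariate and one phrase in 6.6 counts it as a secondary outcome

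*Combined protocol and SAP*

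**What the plan says.** **Covariate role.** Section 6.3 states a dual purpose for its list. The first part is "Self-reported behavioral and motivational measures will be collected to use as covariates in multivariable analysis"; the second is exploratory correlation. One item on the list is "Healthy eating inventory". No other diet score exists in the plan, so this must be the Healthy Eating Index of 5.1.6. The HEI row of Table 1 (Analysis plan, in 6.5.3) reads "Mean/SD or median/IQR, ANCOVA covariate, Pearson/Spearman correlation with demographic variables". The rows for the delay-discounting parameter k and the relative autonomy index (RAI) tie the same role to a baseline value: "ANCOVA covariate (visit 1 measure".

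**Timing.** Section 4.3.2 places randomisation at Visit 2: "Randomize to 1 of 16 experimental conditions". Section 4.4.1 schedules "2 weekday, 1 weekend recall during weeks 1-2 of intervention", and 5.1.6 agrees: "During weeks 1-2 of the intervention, three 24-hour (2 weekday, 1 weekend) dietary recall interviews of participants will be conducted". Section 3.1.4 and the Schedule of Study Procedures give the same timing. There is one set of recalls.

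**Models that could take a covariate.** For MVPA, steps, BMI Z-score and the laboratory outcomes, Table 1 gives "Mean/SD or median/IQR, ANOVA/ANCOVA" without listing covariates. The ANOVA described in 6.5.1 names none. Section 6.4 lists adjustment variables without HEI, but the list is worded as open.

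**Outcome role.** The power statement in 6.6 groups HEI with BMI Z-score and laboratory values as secondary outcomes. HEI is in neither 2.2 nor 6.2. Section 6.3 is headed as exploratory, and Table 1 has no comparison of HEI by factor.

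**The concern.** The objective is the total effect of each factor and their interactions. A covariate fixed before randomisation leaves that estimand unchanged. One measured after the factors have started to act may carry part of a factor's effect, or may share unmeasured causes with the outcome. Adjusting for it then answers a different question, and the shift can go either way. The plan applies the baseline restriction to k and RAI. The HEI row has no such restriction and could not have one, because there is no baseline HEI.

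The open choice between ANOVA and ANCOVA also leaves room to decide, once data are in hand, between models with and without HEI that estimate different things. Section 6.5.1 judges effects against a 15-minute threshold, so the estimand should be fixed in advance.

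The 6.6 phrase adds a smaller inconsistency. If HEI were an outcome that the factors might move, that would itself be a reason not to adjust for it.

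**Working it through.** **Step 1. Is there a pre-randomisation HEI?** The abstract mentions nutrition among assessments at the two in-person visits. The Visit 1 procedures (4.2), the questionnaires (5.1.7) and the Schedule of Study Procedures contain no diet instrument at Visit 1, and 5.1.6 calculates HEI from the weeks 1-2 recalls. So there is no baseline HEI. With a single measurement, HEI also cannot be a Visit 1 to Visit 5 change, the form 6.2 gives to the clinical and laboratory endpoints.

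**Step 2. Reproduce the plan's power figures.** Inputs from 6.6: N = 64, two-sided alpha 0.05, difference 15 min, SD 20. With -1/+1 coding the standardised coefficient is 15/(2 × 20) = 0.375, shown as 0.38. The noncentrality is 0.375 × √64 = 3.0. With 64 - 5 = 59 residual df (intercept and four main effects) power is 0.839; Table 2 says 0.84. For the secondary outcomes, 0.36 × 8 = 2.88 gives 0.809 against the stated 0.80. Both reproduce, and neither depends on whether HEI is named.

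**Step 3. What adjustment for HEI would do.** Two inputs are assumptions, not in the documents: rho, the within-level correlation of HEI with the outcome, taken as 0.1-0.3; and d, the difference in HEI between the two levels of a factor in SD units, taken as 0-0.2 because no factor is described as targeting diet.

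- Adjusted effect = 15 - rho × 20 × d
- Standard error = (2 × 20/√64) × √(1 - rho²) × √(1 + d²/4), where the first term is 5.0
- Residual df = 58

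| rho | d | Adjusted effect (min) | Power |
|---|---|---|---|
| 0.1 | 0 | 15.0 | 0.843 |
| 0.3 | 0 | 15.0 | 0.871 |
| 0.1 | 0.1 | 14.8 | 0.832 |
| 0.3 | 0.1 | 14.4 | 0.843 |
| 0.1 | 0.2 | 14.6 | 0.819 |
| 0.3 | 0.2 | 13.8 | 0.808 |
| 0.3 | -0.2 | 16.2 | 0.914 |

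The largest shift is 0.3 × 20 × 0.2 = 1.2 min. The standard error there is 5.0 × √0.91 × √1.01 = 4.79, so the shift is about 1.2/4.79 = 0.25 of a standard error. A simulation of 8,000 balanced trials with four participants per condition gave 13.87 min and power 0.802 for rho 0.3, d 0.2.

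For BMI Z-score and laboratory outcomes the bias is rho × d SD, that is 0.01-0.06 SD for d of 0.1-0.2. The 0.36 coefficient is a level difference of 0.72 SD, so this is 0.01/0.72 = 1.4% to 0.06/0.72 = 8.3% of it. Power is then 0.77-0.81 against 0.809 unadjusted.

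**The case against.** The strongest reply is that HEI may never enter a model that matters. Section 6.4 is where the plan says what multivariable models adjust for, and it names demographic, disease and baseline variables, plus motivation and delay discounting if imbalanced. HEI is not among them. Section 8.1.1 considers adding only variables that differ at baseline. The ANOVA in 6.5.1 has no covariates. Section 6.3 allows correlational use, so being on its list does not by itself make an item a covariate. This stands as a limit on reach. It does not remove the point, because the 6.4 list is open and the HEI row of Table 1 names the covariate role without saying for which model.

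A reader might infer that the primary MVPA estimate is planned with HEI in the model and will be biased. The documents do not support that: no passage assigns HEI to a particular model, and without an effect of a factor on early diet there is no bias.

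A reader might also infer that the status of HEI as an outcome cannot be determined. That is too strong. The abstract, the synopsis, 2.2, 6.2, 6.3 and Table 1 all leave it out of the secondary endpoints; only one phrase in 6.6 is out of line.

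On post hoc model choice, the open ANOVA/ANCOVA label would allow it for any covariate, and the coded factor labels in 8.1.2 partly protect against it. What is specific to HEI is that including it can change the estimand.

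**Conclusion.** The point holds in limited form. It is certain from the text that the only HEI value is post-randomisation, that Table 1 labels it an ANCOVA covariate without the visit 1 limit given to k and RAI, and that 6.6 disagrees with the endpoint lists. Exposure is confined to the ANCOVA or multivariable models allowed for MVPA, steps, BMI Z-score and laboratory outcomes.

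The size of any bias cannot be derived from the documents. It is zero if the factors leave early diet unchanged and probably small otherwise. Under the assumed ranges it is at most 1.2 of 15 minutes in either direction, with power for MVPA staying at about 0.81 or more. The reason to correct it is that the estimand should not depend on an unspecified post-randomisation covariate, not that a large bias is expected. The 6.6 phrase is an editorial slip with no effect on N, alpha or power. The wording should be fixed before analysis.

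**What to change.** 1. In 6.4 and Table 1 (Analysis plan), state that covariates in any model of factor effects are limited to values measured before randomisation.
2. Delete the covariate entry from the HEI row of Table 1 and the covariate role of HEI in 6.3. Keep HEI as a descriptive and exploratory measure, and use one name for it throughout.
3. Remove HEI from the secondary-outcome sentence in 6.6.

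The cost is wording only; visits, recalls and sample size stay as they are. What is given up is at most a slight gain in precision. If the factors do not affect diet, adjusting for HEI would cut the standard error from 5.0 to between 5.0 × √0.91 = 4.77 and 5.0 × √0.99 = 4.97 min, and raise power from 0.839 to between 0.843 and 0.871, for rho of 0.1-0.3.

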### 6.4 Control of Bias and Confounding

Potentially eligible subjects will be stratified by sex and age (13-18, 19-22), and an equal number of participants will be contacted per group until recruitment goals are reached or all potentially eligible subjects in a category are enrolled or decline to participate.

Multivariable models will adjust for covariates including age, sex, race, ethnicity, disease type (prediabetes versus diabetes), baseline laboratory values, anthropometrics (e.g. BMI-Z), and baseline activity level. The distribution of measured motivation characteristics and delay discounting tendencies will be assessed across intervention components (e.g., proportion with high measures of intrinsic motivation among those randomized to loss-framed versus those randomized gain-framed incentives) will be assessed. If imbalanced across components, these measures will be included in multivariable models.

## 6.5 Statistical Methods

### 6.5.1 Analysis of Primary and Secondary Outcomes of Interest

Descriptive and visual statistics: Demographic and clinical characteristics of subjects will be described using summary statistics, including means, standard deviations, medians, and ranges for continuous variables, and frequencies and percentages of participants for categorical variables. Data will be assessed for outliers. Scatter plots and box plots will be used to examine the relationship between independent (e.g. individual characteristics such as age, prediabetes versus T2D, race/ethnicity; as well as component level, such as gain versus loss-framed incentives) and dependent variables. Line plots will be generated for the primary outcome of daily MVPA, with one line per subject and an overall trend line. Longitudinal data will be summarized by factor level (e.g. loss-framed versus gain-framed incentives). Statistical analyses will be conducted using Stata 17 (StataCorp, College Station, TX) or R: A language and environment for statistical computing (R Corp Team, Vienna, Austria). The significance level for two-sided hypothesis testing will be set at 0.05.

Main Effects and Interactions: The trial is a  $2^4$  full factorial design (4 factors with 2 levels each), resulting in 16 experimental conditions. **Importantly, this is not a 16-arm randomized control trial:** in factorial designs, subjects are “recycled,” allowing for the N per level (e.g. subjects randomized to loss-framing) to be the relevant value rather than the n per experimental condition.(Collins 2018) Effect coding will be used to represent each factor level (e.g. -1 for loss-framed and +1 for gain-framed).(Collins, Dziak et al. 2014) Effect coding allows effect estimates to be uncorrelated when the factorial study is balanced, which allows hypothesis tests to be independent.(Collins 2018) With effect coding, beta coefficient standard errors are equal, so in a balanced design, the power to detect each coefficient is the same.

In addition to ANOVA to evaluate effects of the intervention on MVPA at fixed time points (0 versus 12 weeks, 0 versus 6 weeks, Visit 1 versus Visit 5), mixed effects linear regression models will be created, including interactions found to be significant in ANOVA. These models are implemented via maximum likelihood and account for within- and between-subject variability.(Hedeker and Gibbons 2006) Random intercepts will be used to allow for variation between subjects. Sensitivity of the primary analysis to choice of variance model will be examined.

**Table 1** summarizes the analyses planned by outcome measure.

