#### 6.6 Sample Size and Power

To determine sample size, the MOST R package (FactorialPowerPlan) was used.(Collins, Huang et al. 2017) Using a sample size of 64, 4 factors (n=16/factor, n=4/experimental condition), and two-sided alpha = 0.05, we will have at least 80% power to detect a 15-minute change in MVPA assuming a standard deviation of 20 minutes(Kriska, Delahanty et al. 2013) (**Table 2**). To allow for 64 evaluable subjects, we will recruit 75 AYA (anticipated dropout rate of 15%). In 2020, the Children's Hospital of Pittsburgh Division of Pediatric Endocrinology, Metabolism, and Diabetes followed approximately 2200 patients, approximately 10% (~220) of whom have type 2 diabetes. The vast majority of youth with type 2 diabetes are in the adolescent age range that will be targeted in this intervention. In addition, a variable number of youth with prediabetes are seen by the Division. Based on this, a total sample size of 75 is feasible to enroll over the planned study period. For secondary outcomes including BMI Z-score, labs, and Healthy Eating Index, using a sample size of 64, 4 factors, and two-sided alpha = 0.05, we will have at least 80% power to detect a standardized regression coefficient of 0.36.

**Table 2.** Effect size and power estimates (N=64)

Δ	SD	Effect size	α	Power
15	20	0.38	0.05	0.84
15	20	0.38	0.1	0.91

-	-	0.36	0.05	0.80
-	-	0.32	0.1	0.80

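### The supplementary mixed models are specified as maximum likelihood with about 64 participants and no small-sample correction, so nominal 5% tests of week-averaged component effects run at about 6.5% to 9%, and higher with many covariate columns

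*Combined protocol and SAP*

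**What the plan says.** Section 6.5.1 makes ANOVA on the change in MVPA the main analysis and then adds a second set of models. The sentence that introduces them opens "In addition to ANOVA to evaluate effects of the intervention on MVPA at fixed time points" and goes on: "mixed effects linear regression models will be created, including interactions found to be significant in ANOVA". On estimation it says: "These models are implemented via maximum likelihood and account for within- and between-subject variability". On the random part: "Random intercepts will be used to allow for variation between subjects". The only robustness check named is this: "Sensitivity of the primary analysis to choice of variance model will be examined".

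Section 6.4 describes the adjustment: "Multivariable models will adjust for covariates including age, sex, race, ethnicity, disease type (prediabetes versus diabetes), baseline laboratory values", followed by anthropometrics and baseline activity. For the motivation and delay-discounting measures it adds: "If imbalanced across components, these measures will be included in multivariable models". Section 6.6 sets the size: "To allow for 64 evaluable subjects, we will recruit 75 AYA".

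The documents do not state any of the following:
- REML or a small-sample degrees-of-freedom method
- the reference distribution for the tests
- the number of fixed-effect columns
- whether the tested term is a factor effect averaged over weeks or a factor-by-week effect

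**The concern.** Each factor and each baseline covariate takes one value per participant. The precision of a week-averaged effect therefore rests on a between-person variance estimated from about 64 people, however many Fitbit days each contributes. Maximum likelihood divides the between-person residual sum of squares by N and makes no allowance for the fixed effects already fitted. The resulting standard error is too small even when a random intercept is exactly the right model. Trying other variance structures, as Section 6.5.1 plans, leaves that divisor as it is.

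Intervals for component effects would be too narrow and too many components would look significant. The ANOVA uses residual degrees of freedom, so the two analyses could disagree on significance only because of the divisor. Section 6.5.4 points to the mixed models as the route to an intention-to-treat analysis with incomplete data, so readers may lean on them.

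**Working it through.** **Inputs.** N = 64 evaluable and 75 recruited (6.6); two-sided alpha 0.05 (6.5.1); four two-level factors; eight named covariates or covariate groups (6.4); eight laboratory tests (5.1.4.1).

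**The plan's own figure.** Table 2 gives power 0.84 for 15 minutes with SD 20. The effect-coded coefficient is 15/(2 × 20) = 0.375, and the noncentrality is 64 × 0.375² = 9.0. The noncentral F on 64 - 5 = 59 degrees of freedom gives 0.839, so the stated figure reproduces. It describes a test with residual degrees of freedom. For the mixed models the plan gives no error rate beyond the nominal 0.05.

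**Formula.** In a balanced random-intercept model, a week-averaged between-person effect is estimated by least squares on the person means. With p between-person columns including the intercept:

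- ML variance = RSS/N; unbiased variance = RSS/(N-p)
- ratio of standard errors = sqrt((N-p)/N)
- true size of a nominal 5% Wald z test = P(|t on N-p df| > 1.96 × sqrt((N-p)/N))

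**Column counts.** The four factors and intercept give p = 5. Eight covariates at one column each give p = 13. Entering all eight laboratory tests with the seven other covariates gives 1 + 4 + 7 + 8 = 20. Multi-level race, the conditional motivation and discounting measures, or a carried interaction could bring it to about 25. The counts above 5 are assumptions about how the covariates would be coded.

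| p | SE ratio, N=64 | 1.96 × ratio | Size, N=64 | Likelihood-ratio test, N=64 | Size, N=75 |
|---|---|---|---|---|---|
| 5 | sqrt(59/64) = 0.960 | 1.882 | 6.5% | 6.1% | 6.2% |
| 13 | sqrt(51/64) = 0.893 | 1.750 | 8.6% | 8.2% | 8.0% |
| 20 | sqrt(44/64) = 0.829 | 1.625 | 11.1% | 10.6% | 9.9% |
| 25 | sqrt(39/64) = 0.781 | 1.530 | 13.4% | 12.8% | 11.6% |

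By subtraction from 100%, a nominal 95% interval at N = 64 covers about 93.5%, 91.4%, 88.9% and 86.6%.

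**Simulation.** With N = 64, 12 weekly values, an assumed intraclass correlation of 0.5 and 10,000 runs per setting, the size was 6.6% at p = 5, 8.6% at p = 13 and 12.0% at p = 23. Every setting tried agreed with the formula to within one percentage point. In the same models the factor-by-week test ran at 5.0% to 5.6%.

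**After the change.** REML with a normal reference gives 5.5% at p = 5, 5.6% at p = 13 and 5.7% at p = 25. REML with t on N-p degrees of freedom gives 5.0% in the balanced case.

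**The case against.** Much of the case on the other side stands.

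- **Role.** The mixed models are additional. Table 1 of the analysis plan lists ANOVA/ANCOVA for the primary outcome and no mixed model for any outcome. The 15-minute criterion is a threshold on the estimate, which a wrong standard error does not move. Interactions are screened in the ANOVA, so that step is not inflated.
- **Which term is tested.** The primary outcome is change from baseline. If baseline enters as a repeated outcome, the effect of interest is factor-by-week. It is then judged against within-person variance and stays near 5% under a correct random intercept. Ignored person-specific slopes would inflate that test, but that is a different problem and REML does not cure it.
- **Covariate load.** Section 6.4 speaks of multivariable models without saying that the whole list enters the mixed models, and Section 8.1.1 says only that imbalanced covariates will be considered. If none enters, p is about 5 to 7.
- **Reference and N.** The normal reference is an inference. Participants with partial data also contribute, so N may exceed 64; 75 is the ceiling.

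A reader might infer that the error rate could reach about 17%. That figure (16.9% at N = 64) needs about 31 between-person columns, for instance all ten two- and three-way interactions plus some 16 covariate columns. Section 6.5.1 carries forward only the interactions significant in the ANOVA, so the documents do not describe such a model.

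These points limit the scope and size. They do not remove the defect: the plan names maximum likelihood, and week-averaged component effects from it have standard errors that are too small at any p considered here. Likelihood-ratio tests do not escape it.

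**Conclusion.** The point holds for week-averaged factor effects and interactions in the supplementary mixed models. At N = 64 a nominal 5% test runs at about 6.5% with the factors only and 8.6% with eight one-column covariates. It runs at about 11% to 13% only if coding expands the model to 20 to 25 columns. At N = 75 the figures are about 6.2%, 8.0% and 10% to 12%. They rest on balanced weekly data, a correct random intercept and Wald tests with a normal reference.

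It would be wrong to infer that the trial's primary conclusion is at risk, or that every mixed-model test is inflated. The primary ANOVA/ANCOVA, the 15-minute criterion and factor-by-week tests under a correct random intercept are unaffected. This is a modest error in a supporting analysis, worth correcting because the correction costs so little.

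**What to change.** In Section 6.5.1, replace the maximum-likelihood clause with: *estimated by restricted maximum likelihood (REML), with Kenward-Roger or Satterthwaite degrees of freedom for fixed-effect tests and intervals*. Keep maximum likelihood only for likelihood-ratio comparison of models that differ in their fixed effects. It would help to state in the same place whether the tested term is the week-averaged factor effect or the factor-by-week effect, and which covariates enter and in how many columns.

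The cost is a sentence or two of text. Both named packages support the method, and no data, procedure or sample size changes. In the balanced case, intervals for week-averaged effects become about 6% wider at p = 5 (2.001/1.882, the t quantile on 59 degrees of freedom over the value in the table) and about 15% wider at p = 13 (2.008/1.750, on 51 degrees of freedom). That is the width needed for the nominal 95% coverage.
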